## **Comparison between single shot versus continuous infraclavicular brachial plexus block for postoperative analgesia after distal radius fracture, a prospective randomized open label study**

Pain control following fracture surgery is closely associated with overall patient satisfaction (1). Systemic analgesia (intravenous or oral) are not site specific and may be associated with undesirable side effects such as nausea, constipation, and pruritus. Peripheral blocks provide not only intraoperative anesthesia and pain control but also offer the advantage of lasting analgesic effect into the post-operative period. However, as these blocks wear off, some patients experience a high level of pain. This "rebound phenomenon" has been described and is considered by some authors as one of the shortcoming of single shot peripheral nerve blocks in multiple orthopedic surgical settings (2). Extension of the analgesic benefits of the peripheral nerve blocks can be achieved in the ambulatory settings using continuous perineural ambulatory catheters (3). Use of regional anesthesia for repair of distal radius fracture has been associated with improved pain scores and improved functional outcomes when compared to general anesthesia (4). The impact of extension of these benefits in the settings of distal radius fractures on patient satisfaction, the quality of pain management, quality of recovery, and functional outcome is not entirely known. This study aims to compare the effect of single shot infraclavicular brachial plexus blocks to continuous peripheral nerve blocks on pain scores after surgery.

### **Study Objectives:**

- 1- Measure visual analogue scores every 8 hours for 72 hours after surgery. Pain scores will be recorded by patients in a pain diary (see appendix)
- 2- Measure opioid requirements for the first 3 days after surgery
- 3- Measure patient satisfaction with their pain management.
- 4- Measure the quality of recovery (QOR) at 24 and 72 hours. using the QOR-9 questionnaire.( see appendix)
- 5- Measure the quality of sleep in the first two nights after surgery using a sleep questionnaire ( see appendix)
- 6- Functional outcomes will be assessed at 3 months follow up during the office visit or through administration of the disability assessment of shoulder and hand questionnaire, range of motion of the wrist and fingers will be recorded. (see appendix)

This study tests the hypothesis that patients receiving continuous ICB will have lower pain scores, will use less opioids, will sleep better the first two nights after surgery and will be more satisfied with their pain control regimen after surgery.

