**Randomization:**

A computer generated randomization table will be used for patient allocation to one of the two study groups; The SS group, or the CICB group. Randomization will be done in blocks of 10 patients. Patients' assignments will be written in a sealed envelope that is only open after patient consent for the study.

The study will be unblinded. Patients, nurses in the recovery room, and the research coordinator will be aware of the nature of patient assignment. **Currently, most patients presenting with distal radius fracture at PPMC will receive a single shot brachial plexus block for intraoperative anesthesia. We offer the continuous block option to patients with history of chronic pain or previous adverse reactions to oral opioids. Also these practices may vary depending on surgeon and anesthesiologist preference. Access to analgesic medications will not be restricted by any means for both study groups because of the study procedures.**

**Statistical Analysis:** Statistical analyses will be preformed using STATA 13 statistical software, Dallas, TX. Demographic data will be analyzed using student's T test or fisher's exact test as appropriate. Repeated measurements (pain scores) will be analyzed by repeated measures ANOVA or ANOVA on ranks, with further paired comparisons at each time interval performed using the t-test or Mann-Whitney U-test as appropriate. Categorical data will be analyzed using X analysis or Fisher's exact test where

applicable. Normally distributed data will be presented as means  $\pm$  SE of the mean (SEM), non normally distributed data are presented as medians  $\pm$  quartiles (interquartile range) and categorical data will be presented as raw data and as frequencies. The  $\alpha$  level for all analyses was set as  $P<0.05$ .

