**Sample Size Calculation:** A power analysis done prior to enrollment showed that the number of patients needed to detect a 1-point change in pain score ( $p<0.05$  significance level) was thirty-eight patients. While a 1-point change in pain score may not be clinically significant, we wanted the study to have enough power to detect between a 1-2 point pain score difference. Assuming a dropout rate of 20%, we will enroll fifty patients. Sample size estimate followed a previously published study comparing single shot versus continuous popliteal block for pain control after ankle fracture (5).

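### One hypothesis spans four outcomes, all tested at 0.05, but no outcome is designated primary and no rule says which results would support it

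*Combined protocol and SAP*

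**What the plan says.** All references are to the combined protocol and SAP.

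- **Opening section.** The aim concerns pain alone: "This study aims to compare the effect of single shot infraclavicular brachial plexus blocks to continuous peripheral nerve blocks on pain scores after surgery". The same section also mentions satisfaction, quality of recovery and function as matters not yet well understood.
- **Study Objectives.** Six numbered items are listed, none called primary or secondary. The hypothesis follows: "This study tests the hypothesis that patients receiving continuous ICB will have lower pain scores, will use less opioids, will sleep better" in the first two nights, "and will be more satisfied with their pain control regimen after surgery". That makes four domains in one sentence.
- **Statistical Analysis** (within the Randomization section). The alpha "level for all analyses was set as" P<0.05. No order of testing, adjustment or success rule is given, and the tests are not said to be one- or two-sided. Pain is to be analysed by repeated-measures ANOVA or its rank version, with further comparisons at each time interval.
- **Sample Size Calculation.** Only pain is sized: "the number of patients needed to detect a 1-point change in pain score" at that level "was thirty-eight patients". No numerical power and no SD are given.
- **Measurements.** The six items are repeated, again without ranking.

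**The concern.** The plan does not say what pattern of results would support its hypothesis. Three readings are open: all four domains must favour the continuous block, any one is enough, or pain alone decides. They carry different error rates and different power, and the choice could be made after the data are seen.

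The domains could easily disagree. Analgesic access is unrestricted in both groups, so patients may take opioids until their pain is similar, leaving a difference in opioid use and none in pain. A chance result on sleep or satisfaction could likewise be presented as support when pain shows nothing. Under an all-four reading, a real benefit could fail because one of the unsized outcomes missed significance.

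**Working it through.** **The plan's own figure.** The 38 cannot be reproduced, because neither SD nor power is stated. Solving SD = 1 / [(z_alpha + z_power) × √(2/n)] for a 1-point difference, two-sided 0.05:

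- 38 in total (n = 19 per arm), 80% power: 1 / [(1.96 + 0.84) × √(2/19)] = 1.10
- the same at 90% power: 0.95
- 38 per arm, 80% power: 1.56

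Dropout: 38 / 0.8 = 47.5, so 48, close to the 50 planned. This step is sound. The calculation concerns pain only.

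**Inputs for the four domains.** Number of domains: 4 (Study Objectives). Alpha: 0.05 each (Statistical Analysis). Assumed, because the documents are silent: two-sided tests, one test per domain, equal pairwise correlation r between the test statistics, and equal power per test of 80% or 90%.

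**Any-of-four reading, no true effect on any outcome.** If independent:

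- either direction: 1 − 0.95⁴ = 18.5%
- favouring the continuous block: 1 − 0.975⁴ = 9.6%

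The benchmark for the second figure is 2.5%, the chance that a single two-sided 0.05 test errs in that direction.

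**All-four reading.** The joint claim needs every test to succeed, so its error cannot exceed that of any one test and alpha is not inflated. Joint power if independent is 0.8⁴ = 41% or 0.9⁴ = 66%.

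**Correlated cases.** One million draws of four equally correlated normal statistics; for power, each has mean 1.96 + 0.84 = 2.80 (80%) or 1.96 + 1.28 = 3.24 (90%).

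| r | Any of four, either direction | Any of four, favouring continuous | All four, 80% each | All four, 90% each |
|---|---|---|---|---|
| 0 | 18.5% | 9.6% | 41% | 66% |
| 0.3 | 17.4% | 8.7% | 50% | 71% |
| 0.5 | 15.5% | 7.8% | 56% | 74% |
| 0.7 | 13.0% | 6.5% | 62% | 78% |
| 0.8 | 11.4% | 5.7% | 66% | 81% |

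At r = 0.9 the two error columns are 9.4% and 4.7%.

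**One test per domain is a low count.** Pain every 8 hours for 72 hours gives 72 / 8 = 9 time points. Nine independent tests at 0.05 give 1 − 0.95⁹ = 37%. Naming pain as primary therefore settles nothing unless one pain test is also named.

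**What each rule would need**, if 38 gives 80% power and all four outcomes share the same standardized effect:

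- One primary, or a fixed order: N unchanged.
- Any of four at 0.05 / 4 = 0.0125 each: N × 1.42, so 54 evaluable and 54 / 0.8 = 67.5, 68 enrolled. With N kept at 38, power per test falls from 80% to 62%.
- All four with 80% joint power, independent: each test needs 0.8^(1/4) = 94.6% power, N × 1.62, so 62 evaluable and 62 / 0.8 = 77.5, 78 enrolled.

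**The case against.** The strongest reply is that pain is already primary in substance: it is the only outcome in the aim, the only one sized, and first in both lists. This stands in part. It makes the remedy short and points to the right outcome. It does not close the gap, because the sentence that states the hypothesis widens it to four domains and the alpha rule treats every analysis alike. An implied primary does not prevent a later choice.

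A second reply is that the claims are joined by 'and', so all four must hold and the error of the joint claim stays within 5%. This is correct. A reader might infer that the plan carries a 13–19% false-positive rate, or that its alpha rule fails for the hypothesis as written. The documents support neither. Inflation arises only under an any-of-four rule that the plan never states. The 13–19% also requires no true effect anywhere, stops at an assumed correlation of 0.7, and counts errors favouring the single shot, which are not the errors that would mislead a reader of this directional hypothesis.

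A third reply is that the joint power figures rest on assumed power. That also stands. The protocol says only that "we wanted the study to have enough power to detect between a 1-2 point pain score difference" and that "Sample size estimate followed a previously published study comparing single shot versus continuous popliteal block for pain control after ankle fracture", so both 80% and 90% are shown, and equal power across four different instruments is a simplification.

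**Conclusion.** The concern holds as a missing primary designation and a missing success rule. It is more than a missing label, because a team following the 0.05-for-everything rule could report any single domain as support.

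The size depends on the reading. If all four are required, the error is controlled but the claim was never sized: 41–62% joint power at 80% per test, 66–78% at 90%. If any one suffices, the chance of a false result for the continuous block is 9.6% to 6.5% rather than 2.5%. Both ranges assume two-sided tests, one test per domain and correlations from 0 to 0.7.

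A reader might also infer that the trial would miss a true four-fold benefit more often than not. That follows only at 80% power per test with low correlation (r = 0 to 0.3 in the table), and the documents establish neither.

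This should be changed, but it does not call the design into question.

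**What to change.** In Study Objectives and in Statistical Analysis:

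1. Name pain as the single primary outcome, decided by one test at two-sided 0.05. One suitable choice is the overall treatment-group effect over 0–72 hours from the repeated-measures analysis already planned. State in advance the condition for using the rank version. Make the comparisons at individual time points descriptive.
2. Label opioid use, sleep and satisfaction secondary, with one pre-stated summary for each. Either report them as supportive with confidence intervals, or test them in a pre-stated fixed order at two-sided 0.05, only if pain is significant and stopping at the first non-significant result.
3. Label quality of recovery, QuickDASH and range of motion exploratory.
4. Reword the hypothesis sentence so that pain decides it and the other three claims are secondary.

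The cost is wording, with no change in the number of patients. The downside is that a secondary benefit, such as lower opioid use, cannot be claimed as confirmed if pain is not significant. A sponsor who prefers another rule can adopt it, but must state it beforehand and size for it. The change controls chance findings only; it does not remove bias from self-reported outcomes in an open-label trial.

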### **Methods:**

**Study design:** prospective, randomized, unblinded study with a parallel design and an allocation ratio of 1 to 1 for the treatment groups.

**Inclusion Criteria:** Patients scheduled for open reduction and internal fixation of a distal

radius fracture with American Society of Anesthesiologists (ASA) physical status I -III, mentally competent and able to give consent for enrollment in the study.

**Exclusion criteria:**

Allergy to local anesthetics. Impaired kidney functions and patient with coagulopathy will be also excluded. Patients opting to go under general anesthesia and those refusing the block will be excluded from the study. Chronic pain syndromes and patients with chronic opioid use defined as use of regular daily doses of systemic narcotics for the past 6 months prior to the surgery. BMI of 40 or more

**Recruitment:**

Patients will be identified from the surgical schedule the day before surgery and will be contacted by one of the study investigators to scan for eligibility for enrollment. Study aims and procedures will be explained to patients. Patients will be consented the morning of their surgery by one of the study investigator or the research coordinator.

25 patients will be enrolled in each study group with a total of 50 patients. Patients will be randomized to one of two study groups.

Group A will be named SS group, group B will be named the continuous infraclavicular block (CICB) group.

**Randomization:**

A computer generated randomization table will be used for patient allocation to one of the two study groups; The SS group, or the CICB group. Randomization will be done in blocks of 10 patients. Patients' assignments will be written in a sealed envelope that is only open after patient consent for the study.

The study will be unblinded. Patients, nurses in the recovery room, and the research coordinator will be aware of the nature of patient assignment. **Currently, most patients presenting with distal radius fracture at PPMC will receive a single shot brachial plexus block for intraoperative anesthesia. We offer the continuous block option to patients with history of chronic pain or previous adverse reactions to oral opioids. Also these practices may vary depending on surgeon and anesthesiologist preference. Access to analgesic medications will not be restricted by any means for both study groups because of the study procedures.**

**Statistical Analysis:** Statistical analyses will be preformed using STATA 13 statistical software, Dallas, TX. Demographic data will be analyzed using student's T test or fisher's exact test as appropriate. Repeated measurements (pain scores) will be analyzed by repeated measures ANOVA or ANOVA on ranks, with further paired comparisons at each time interval performed using the t-test or Mann-Whitney U-test as appropriate. Categorical data will be analyzed using X analysis or Fisher's exact test where

applicable. Normally distributed data will be presented as means  $\pm$  SE of the mean (SEM), non normally distributed data are presented as medians  $\pm$  quartiles (interquartile range) and categorical data will be presented as raw data and as frequencies. The  $\alpha$  level for all analyses was set as  $P<0.05$ .

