**Study procedures:**

In our institution we usually advocate for regional anesthesia and intravenous sedation for the repair of open fracture of the distal radius. Patients will be approached and consented for the study by one of the study staff.

Once consented their group assignment will be revealed to the anesthesiologist assigned to the room who will be performing the block

Patients will be monitored during block performance with standard ASA monitors. All patients will receive 2 L of oxygen via a nasal cannula. Sedatives will be titrated to effect. Midazolam 1-2 mg, and fentanyl 50-100 mcg will be used for sedation.

Block time out will be preformed according to standard operating procedure.

All blocks will be done under ultrasound guidance. Sonosite S nerve machine will be used with a low frequency curvilinear (C5) US probe with 2-5 MHZ frequency. Both single shot and continuous ICB will be performed according to the SOP in our department. Ultrasound survey of the deltopectoral groove below the clavicle will take place. The axillary artery and the three cords (posterior, medial and lateral) of the brachial plexus will be identified in short axis view deeper to the pectoralis minor muscle.

=====

For single shot blocks: A 4 inch 21 gauge single shot (B-Braun) needle will be introduced in-plane towards the posterior cord of the brachial plexus and 1-2 mL of dextrose 5% (D5%) bolus will be used to verify correct placement of the needle in the vicinity of the posterior cord and adequate spread pattern to both lateral and medial cord. 20 ml of Ropivacaine 0.5% will be injected through the needle with intermittent aspiration after each 5 ml bolus injection.

For the continuous block: A 4 gauge 18 inch touhy needle ( B –Bruan) will be introduced towards the posterior cord as above. When the needle tip and the pattern of spread is confirmed using D5% solution, a 21 gauge catheter will be introduced 2 cm beyond the needle tip under ultrasound visualization. The needle will be withdrawn over the catheter. Injection of a total of 20 ml of ropivacaine 0.5% ( in divided 5 ml boluses with intermittent aspiration) will take place through the catheter while observing the spread of local anesthetic under ultrasound. The catheter hub will be affixed to the upper lateral chest with sterile occlusive dressings and an anchoring device.

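### A single stated block size of 10 in an open trial, where a coordinator who knows assignments may take consent, makes some allocations foreseeable: an expected 8.3 of 50 for a fully informed recruiter

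*Combined protocol and SAP*

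**What the plan says.** All references are to the combined protocol and SAP.

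- **Randomization** uses a computer-generated table: "Randomization will be done in blocks of 10 patients". It mentions no second block size, no random variation of size and no stratification.
- **Methods** (study design) gives "an allocation ratio of 1 to 1 for the treatment groups", and **Recruitment** says "25 patients will be enrolled in each study group with a total of 50 patients". Balance of 5:5 within each block is inferred from these; it is not spelled out.
- **Randomization** also says "The study will be unblinded", and "Patients, nurses in the recovery room, and the research coordinator will be aware of the nature of patient assignment".
- **Recruitment**: "Patients will be consented the morning of their surgery by one of the study investigator or the research coordinator".
- **Study procedures**: "Once consented their group assignment will be revealed to the anesthesiologist assigned to the room who will be performing the block".
- The stated safeguard, in **Randomization**, is that "assignments will be written in a sealed envelope that is only open after patient consent for the study".

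The documents do not say who prepares the table, who knows the block size, or whether anyone who takes consent keeps a running count.

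**The concern.** An envelope opened after consent hides the next card. It does not stop anyone deducing that card from the earlier ones when the block size is fixed and known. Here one role, the research coordinator, is stated both to know assignments and to be able to take consent. Nothing in the plan separates those two tasks or withholds the block size from recruiting staff; the size is printed in the protocol.

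If the next assignment can be foreseen, the choice of whom to approach or consent can depend on it, and randomisation no longer protects the comparison. Staff may have a reason to prefer one group for some patients. The Randomization section says that outside the trial the continuous block is offered to patients with earlier adverse reactions to oral opioids, and that practice varies with surgeon and anesthesiologist preference. The exclusion criteria remove chronic pain but not previous opioid reactions, and opioid use is a study outcome. Pain scores are recorded by unblinded patients, so blinded assessment gives no second line of defence.

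**Working it through.** **Inputs.** Block size 10 (Randomization); 1:1 ratio (Methods); 25 per group and 50 in total (Recruitment), hence five complete blocks. Assumed: 5:5 within each block.

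**The plan's own figure.** The documents state no predictability figure. The denominator of 50 comes from Sample Size Calculation: 38/(1 − 0.20) = 47.5, rounded up to 48. The planned 50 is the next multiple of 10.

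**1. Assignments that are certain, full knowledge.** The recruiter knows the block size, the block boundaries and every earlier assignment. In a block of 2m, an assignment is certain once one group has used its m places. The number certain, T, has P(T = t) = 2·C(2m−t−1, m−1)/C(2m, m), with mean 2m/(m+1).

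- Block of 10 (m = 5): 10/6 = 1.667. Enumerating all 252 sequences gives the same mean, with probabilities 0.556, 0.278, 0.119, 0.040 and 0.008 for T = 1 to 5.
- Five blocks: 5 × 1.667 = 8.33 of 50 (16.7%), SD 1.99, 2.5 to 97.5 percentiles 5 to 13. The last patient of every block is always certain, so the minimum is 5.
- One list of 50 (m = 25): 50/26 = 1.92 of 50.

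**2. Best guess, full knowledge.** The recruiter guesses the group with more places left. Correct guesses above chance are 2^(2m−1)/C(2m, m) − 0.5 per block.

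- Blocks of 10: 512/252 − 0.5 = 1.532 per block, 7.66 per 50. Correct: (25 + 7.66)/50 = 65%.
- One list: 3.95 per 50. Correct: (25 + 3.95)/50 = 58%.

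**3. Incomplete tally.** This was simulated with 40,000 blocks and 20,000 lists. Each earlier assignment is seen independently with the probability shown, and the recruiter guesses the group seen less often.

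| Earlier assignments seen | Certain of 50: blocks of 10 | Certain of 50: one list | Best guess: blocks of 10 | Best guess: one list |
|---|---|---|---|---|
| 100% (exact) | 8.3 | 1.9 | 65% | 58% |
| 90% | 4.9 | 0.1 | 63% | 56% |
| 75% | 2.0 | 0.0 | 60% | 55% |
| 50% | 0.3 | 0.0 | 57% | 53% |

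**4. Illustration of bias.** Assume a full tally acted on at every slot, and a prognosis gap of 0.25 to 0.5 SD between patients steered to each group. The gap is an assumption; the documents give nothing to set it by. Shift = gap × 2 × excess correct guesses/50.

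- Blocks of 10: 2 × 7.66/50 = 0.306, so 0.08 to 0.15 SD.
- One list: 2 × 3.95/50 = 0.158, so 0.04 to 0.08 SD.

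**5. Price of one list if accrual stops at 40.** The number in one arm is hypergeometric (50, 25, 40). The expected arm difference is 2.2 patients, and 6 (23:17) is the smallest bound that covers 95%. With blocks of 10 the difference is 0. At 23:17 the variance ratio is (1/23 + 1/17)/(1/20 + 1/20) = 1.023.

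**The case against.** The strongest reply is that 8.3 is a ceiling. It needs a recruiter who knows the block size, the boundaries and every earlier assignment, and the documents attribute that knowledge to nobody. Consent may be taken by any of several people, and each assignment goes to the anesthesiologist in that room, so investigators need not see them all. At 50% seen, almost nothing is certain. This stands as a limit on size. It does not clear the coordinator, who is named as aware of assignments and may take consent.

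Ten is also not a small block. Fixed blocks of 6 or 4 would be worse (12.5 and 16.7 of 50). That is right: the weakness is one fixed size together with who may know it, and shorter blocks are no remedy.

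Room to steer is limited. Patients come from the surgical schedule, several eligibility criteria are objective, and 50 patients over about 12 months is roughly one a week. Discretion remains at approach and consent, however, and slow accrual makes a tally easy to keep.

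The bias illustration is generous. If only the certain slots were steered, the shift would be 8.33/50 × gap, or 0.04 to 0.08 SD. Even 0.08 to 0.15 SD is only 0.27 to 0.54 of a standard error with 25 per group (√(2/25) = 0.283 SD), which would take a two-sided 5% test to about 5.8% to 8.3%. This stands: the likely distortion is modest.

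Finally, simply hiding the block size from recruiters would address the mechanism without a new list. It would help, and it is part of the fix. One list adds protection if the scheme becomes known, because it is less predictable at every level of knowledge examined.

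**Conclusion.** The concern holds. The plan combines one fixed block size, open allocation and a role that may both know past assignments and take consent, and the envelope does not close that gap. For a fully informed recruiter, an expected 8.3 of 50 assignments are certain, against 1.9 with one list. With three quarters of the tally the figures are 2.0 against 0.0.

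These figures rest on 5:5 balance within blocks and known block boundaries; the upper figure also needs a complete tally. The size in SD units rests on an assumed prognosis gap and full exploitation, so it is illustrative only. Nothing in the documents shows that anyone would count or steer. The change is worth making because it is cheap and the plan describes no stratification or interim analysis that needs balance every ten patients. It is not a flaw that invalidates the design.

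**What to change.** Before enrolment begins, replace the five blocks of 10 with a single permuted list of 50 (25 SS, 25 CICB), prepared by someone who does not recruit. Keep the restriction scheme out of the version of the protocol that recruiting staff use. The final split at 50 is unchanged.

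The cost is one re-run of the randomisation table and one sentence of text, with no extra patients or staff. Balance during accrual is looser. If enrolment stopped at 40, the expected arm difference would be 2.2 patients, and a 23:17 split would raise the variance of the group difference by 2.3% over 20:20. One list reduces predictability but does not remove it.

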#### **Measurements:**

- 1- Visual analogue scores every 8 hours for 72 hours after surgery. Pain scores will be recorded by patients in a pain diary
- 2- Measure opioid requirements for the first 3 days after surgery
- 3- Measure patient satisfaction with their pain management.
- 4- Measure the quality of recovery at 24 and 72 hours
- 5- Measure the quality of sleep in the first two nights after surgery. sleep quality questionnaire is adapted from the insomnia severity index (6) and we added

another questions asking about the frequency of waking up at night because of pain after surgery (7, 8)

6- Functional outcomes will be assessed at 3 months follow up during the office visit or through administration of the quick disability assessment of shoulder and hand (DASH) questionnaire (9), range of motion of the wrist and fingers will be recorded.

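### Nine diary pain scores per patient go into repeated measures ANOVA with no rule for missed entries and no sphericity correction; a mixed model on all recorded scores would close both gaps

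*Combined protocol and SAP*

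**What the plan says.** Measurements, item 1, sets the schedule and the recorder: "Visual analogue scores every 8 hours for 72 hours after surgery. Pain scores will be recorded by patients in a pain diary". Study Objectives, item 1, says the same. At 72/8 this is nine scores per patient, or ten if a time-zero score is also taken, which the text does not say.

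The Statistical Analysis paragraph (printed under Randomization) gives the analysis: "Repeated measurements (pain scores) will be analyzed by repeated measures ANOVA or ANOVA on ranks", followed by tests at single times, "with further paired comparisons at each time interval performed using the t-test or Mann-Whitney U-test as appropriate". On software it says "Statistical analyses will be preformed using STATA 13 statistical software". It says nothing about missed entries, the form in which the ANOVA is fitted, the within-patient covariance or a sphericity correction.

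The Sample Size Calculation needs 38 patients for a 1-point difference in pain score and then allows for losses: "Assuming a dropout rate of 20%, we will enroll fifty patients". It does not say whether that allowance covers incomplete diaries as well as withdrawals. It gives no SD and no power.

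**The concern.** Pain score is the first-listed outcome and the only one on which the trial is sized. Patients fill in the diary themselves over three days, largely at home, on an 8-hourly schedule, so some missed entries are plausible. Repeated measures ANOVA can be fitted in more than one way, and the ways treat an incomplete diary differently:

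- In its wide or multivariate form it needs all nine scores, so one missed entry removes the patient.
- On stacked rows, one row per score, only the missed row is lost. The data are then unbalanced and the between-group F test no longer has an exact error term.

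The plan does not choose. In an unblinded trial that leaves the choice open until the data have been seen.

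Separately, the univariate within-patient tests assume sphericity, meaning equal variance of the differences between any two times. Scores spread over 72 hours are unlikely to satisfy this, because neighbouring scores are usually more alike than distant ones.

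**Working it through.** **Inputs from the document.** Nine scores per patient; 38 patients needed; 20% dropout; 50 enrolled, 25 per arm; alpha 0.05.

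**Assumed, because the document gives no figure.** The missed-entry rate m, how misses are distributed over patients, two-sided testing, the SD, the power and the within-patient correlation.

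**1. The plan's own enrolment figure.** 38/0.8 = 47.5, so 48, which is within two patients of 50. Conversely 50 × 0.8 = 40 patients are expected to remain. The dropout step holds. The figure of 38 cannot be reproduced without an SD and power. Solving backwards for 80% power, SD = √(19/2)/(1.960 + 0.842) = 1.10.

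**2. Complete diaries if misses are independent.** The share complete is (1 − m)^9.

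| m | share complete | of 50 | of 40 |
|---|---|---|---|
| 2% | 0.834 | 41.7 | 33.3 |
| 5% | 0.630 | 31.5 | 25.2 |
| 10% | 0.387 | 19.4 | 15.5 |

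**3. Missed-entry rate at which 38 complete patients are expected.**
- After 20% other dropout: 1 − (38/40)^(1/9) = 0.57%, about 2 of 360 entries.
- With no other dropout: 1 − (38/50)^(1/9) = 3.0%, about 13 to 14 of 450 entries.
- With ten scores instead of nine the limits are 0.51% and 2.7%.

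**4. Complete diaries if misses cluster within patients.** In a beta-binomial model with intra-patient correlation ρ, let s = 1/ρ − 1, a = ms and b = (1 − m)s. The share complete is the product over i = 0 to 8 of (b + i)/(a + b + i). At an assumed ρ = 0.5:

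| m | share complete | of 50 | of 40 |
|---|---|---|---|
| 2% | 0.945 | 47.2 | 37.8 |
| 5% | 0.866 | 43.3 | 34.7 |
| 10% | 0.747 | 37.4 | 29.9 |

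**5. Illustrative power under complete-case analysis.** With 5% of entries missed independently, the standard error rises by 1/√0.63 = 1.26.
- SD 1.10, 1-point difference, normal approximation: 82% with 20 per arm; 63% with 20 × 0.63 = 12.6 per arm.
- Single-score SD 2, within-patient correlation 0.5: the SD of a nine-score mean is 2√((1 + 8 × 0.5)/9) = 1.49. For a 1.5-point difference (noncentral t), power falls from 87% to 68%. With these inputs, 20 per arm would give only 54% at 1 point, so they are not the plan's inputs.

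**6. Illustrative bias under complete-case analysis.** In simulations where the chance of a miss rises with the previous score, the arm difference was biased towards zero. The bias was about 1-4% at a log-odds slope of 0.2 per point and about 6-15% at 0.4. Likelihood estimation on all recorded scores showed no material bias in simulations of this kind.

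**7. Sphericity.** Simulated null rejection rates of the uncorrected group-by-time test, 20 per arm, nine scores:
- AR(1) correlation 0.5, 0.7, 0.8, 0.9: 7.3%, 8.6%, 10.1%, 10.5%. A repeat run gave 7.1%, 9.3%, 10.0%, 11.1%.
- Compound symmetry: 5.0%.

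**The case against.** The strongest reply is that the plan nowhere deletes incomplete patients. A reader might infer that one missed entry costs the whole patient, so that 38 evaluable patients survive only if almost nothing is missed. The document does not support that. Deletion belongs to one form of the ANOVA and the form is not stated. The 0.6% limit also requires the whole 20% allowance to be spent on other losses and misses to be scattered. If the allowance is meant to cover unusable diaries, 12 of 50 may be incomplete, and clustering in a few patients tolerates more missed entries. This stands in full, and it is why the loss is stated conditionally and as a range. It does not remove the gap. Study procedures already withdraws patients whose catheter fails and is not re-sited, which uses some of the allowance. Even with clustering, 5% missed leaves fewer than 38 of 40.

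A reader might also infer that stacked rows would give a badly biased answer. Simulation does not bear this out. With patient and time terms and missingness driven by the previous score (4-8% per entry), the bias was below 1% in all eight scenarios tried. What remains against that form is the inexact error term, and no size has been put on it here.

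The tests at single times can use every score available at that time. True, but they follow the overall analysis and do not replace it.

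Finally, the plan does not exclude a sphericity correction. The 7-11% describes the group-by-time test with no correction and AR(1) correlation. It should not be read as the trial's overall type I error.

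**Conclusion.** The concern holds in a limited form. The main pain analysis has no provision for missed entries and no sphericity correction, and how much this matters depends on choices the plan leaves open.

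- On complete diaries, the expected number stays at 38 or more only with at most about 0.6% to 3% of entries missed at random. The two ends correspond to 20% other dropout and none. Clustered misses cost less.
- On stacked rows no patient is lost through a missed entry, but the between-group test is not exact.
- In either form, an uncorrected group-by-time test is too liberal under AR(1) correlation, and correct at 5% under compound symmetry.

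The power and bias figures only illustrate, since the document gives no SD, power or missed-entry rate and nothing to show that misses follow pain. They should not be quoted as properties of this design. The case for change rests on a better method being available at little cost, not on a demonstrated loss of patients.

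**What to change.** In the Statistical Analysis paragraph, replace repeated measures ANOVA for the pain scores by a linear mixed model fitted by restricted maximum likelihood to every recorded score of every randomised patient. Specify:

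- arm, time as nine categories, and arm-by-time;
- a within-patient covariance not restricted to compound symmetry (for example heterogeneous Toeplitz), with a simpler structure named in advance if it does not converge (for example AR(1) plus a random intercept);
- small-sample degrees of freedom, from other software if Stata 13 does not provide them;
- the arm difference averaged over time and at each time;
- a table of missed entries by arm and time.

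If the rank-based version is kept as an alternative, state how it treats missed entries.

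The cost is wording and slightly more analysis work, with no extra patients or data. The downside is possible non-convergence with about 40 patients, which the prespecified fallback handles. Using the same model for quality of recovery, sleep and opioid use is optional and not part of this defect.
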